7. STUDY POPULATION

7.1. Subjects Disposition

Subject disposition will be summarized descriptively as follows:

- A summary of the number of subjects in each of the analysis populations.
- The number and percentages of subjects who signed informed consent but were not treated.
- The number and percentages of subjects who had Bone Marrow Aspiration but were not treated.
- The number and percentage of subjects who (a) completed study (b) discontinued from the study by number of treatments prior to discontinuation. For those who discontinued from the study, the primary reason for discontinuation from the study will be presented.
- If any subjects are re-screened this will be footnoted in the Table along with the Subject-ID.

7.2. Screen Failures

Screen failures are potential study subjects who provide written informed consent authorization and complete some or all screening procedures but are determined to be ineligible for treatment with study drug or decide not to continue prior to first treatment.

7.3. Protocol Deviations

Summary of all important protocol deviations by type of deviations will be summarized in a Table and details provided in a listing.

7.4. Demographic and Baseline Characteristics

The demographic and baseline characteristics data collected at the Screening Visit (V1) will be presented for the Safety population. The continuous variables, ex., age in years, will be summarized using descriptive statistics (n, mean, SD, first quartile, median, third quartile, minimum, and maximum). The discrete variables, ex., gender will be summarized using counts and percentages.

Baseline electrocardiogram (ECG) results will be presented for each subject in a listing.

Baseline vital signs, physical examination and laboratory results will be in the Safety Tables and not separately in the Demographics and Baseline Characteristics sections.

7.5. Listing of Subject Inclusion and Exclusion Criteria

For subjects who did not meet inclusion or exclusion criteria and were not treated, a listing will indicate which criteria they did not meet.

7.6. Medical History and Medical Conditions Present at Entry

Medical history will be coded using the MedDRA, version 21.1. Counts and percentages of subjects with each medical history will be summarized using MedDRA system organ class (SOC) and PT for the Safety population. SOCs will be ordered alphabetically and PTs within SOCs will be ordered by descending incidence of all subjects.

MS Medical History would be presented separately in a listing for each subject. It will include the date of onset of MS symptoms, date of diagnosis of MS, whether MS is Primary Progressive MS (PPMS) or Secondary Progressive MS (SPMS), and if SPMS, date of conversion to SPMS.

7.7. Prior and Concomitant Medications

All medications (e.g., both prior and concomitant) will be coded with respect to the Anatomical Therapeutic Chemical (ATC) drug classification coding system and the data summarized by level 2 and PT. Therefore, all possible ATC codes for a given medication by the WHODD Version September, 2018 will be displayed.

The displays of medications will be performed without any regard to the indication the medication was taken for.

Separate Tables will display prior medications and CMs using the Safety Population.

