Major Exclusion Criteria	
 1. Prior stem cell therapy of any kind. 2. Active participation in any other MS interventional study or of unapproved MS investigational therapy within 90 days prior to the Screening Visit (Visit 1). 3. Inability to lie flat for the duration of intrathecal cell transplantation and/or bone marrow aspiration, or inability to tolerate study procedures for any other reason. 4. History of clinically significant autoimmune disease (excluding thyroid disease) that may confound study results, myelodysplastic or myeloproliferative disorder, leukemia or lymphoma, whole body irradiation, hip fracture, or severe scoliosis. 5. Any unstable clinically significant medical condition other than-multiple sclerosis (e.g., within six months of Screening Visit (Visit 1), had myocardial infarction, angina pectoris, and/or congestive heart failure), any clinically significant coagulopathy, treatment with anticoagulants that, in the opinion of the investigator, would compromise the safety of participants. 6. Any history of malignancy within the previous 5 years, except for non-melanoma localized skin cancers (with no evidence of metastasis, significant invasion, or re-occurrence within three years of Screening Visit (Visit 1)). 7. Current use of immunosuppressant medication or use of such medication within 6 months of study enrollment (aside from approved B-cell immunotherapy). 8. Any history of acquired or inherited immune deficiency syndrome. 9. Pregnant women or women currently breastfeeding. 10. Subjects for whom MRI is contraindicated (i.e., have a pacemaker or other metallic implanted device) or are unable to remain in the machine for period of time needed to acquire a scan. 11. Positive test result for Hepatitis B virus (HBV; surface antigen (HBsAg) and antibodies to core antigen (IgG and IgM anti-HBc)), Hepatitis C virus (HCV), Human Immune deficiency Virus (HIV) 1 and 2.
ASSESSMENTS	
Safety	Changes in vital signs and physical examination findings, hematology, blood chemistry, urinalysis, AEs, and changes in concomitant medications. New MRI lesions (new - or newly enlarging – T1 and T2 weighted images will be evaluated for safety).
Efficacy	Efficacy assessments will be based upon: T25FW, 9-HPT, blood and CSF biomarkers, EDSS, MSWS-12, Physical function measured with wearable sensor, LCLA, and SDMT. The efficacy endpoints are further described in the statistical section below.

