6.2. CONCOMITANT AND EXCLUDED THERAPY

Concomitant medications are those given to the subject during or after the first transplantation. All concomitant medications will be recorded.

Brainstorm Cell Therapeutics Ltd.	IND#018615	
Phase 2 Clinical Protocol BCT-101-US Amendment 1.1, June 2019	MSC-NTF cells (NurOwn®)	Page 36 of 59

Current use of immunosuppressive medication or use of such medication within 6 months of study enrollment (aside from approved B-cell immunotherapy) and anticoagulation therapy are exclusionary.

Alemtuzumab (Lemtrada), Cladribine (NDA submitted), Natalizumab (Tysabri), S1P modulators (such as Gilenya) high dose pulse intravenous methylprednisolone (IVMP, 1 gram) to treat a relapse within the 6 months prior to study entry or other investigative MS therapies are exclusionary due to safety considerations. However, a single dose of IVMP 100 mg as part of the Ocrevus (or Rituxan) infusion protocol q6M is not exclusionary and would be allowed in the study.

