9. ASSESSMENT OF ENDPOINTS

9.1. PRIMARY ENDPOINT

9.1.1. *Safety*

The primary endpoint will be to evaluate the safety and tolerability of 3 intrathecal doses of NurOwn® (MSC-NTF cells).

Safety endpoints include AEs, changes in physical and neurological examination findings, hematology, serum chemistry, urinalysis, vital signs, and requirement of concomitant medications. MRI (Brain T1 and T2 weighted images) will be evaluated for safety.

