3.2. Study Endpoints

3.2.1. Primary Endpoints

Primary endpoints of this study are assessment of safety and tolerability by analysis of changes in vital signs and physical and neurological examination findings, hematology, blood chemistry, urinalysis, AEs, SAEs, MRI data and changes in concomitant medications (CM).

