3.4 Prior and Concomitant Medication

PRIOR AND CONCOMITANT MEDICATIONS

The definition of a prior medication is defined as any medication taken prior to the date of first treatment and either stopped prior to the first treatment or continued after it.

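### Change in concomitant medication is part of the primary safety endpoint, but the two planned medication tables poorly separate new need after dosing from treatment carried on unchanged

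*SAP*

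**What the plan says.** **The endpoint.** SAP 3.2.1 ends its list of primary endpoint components with "AEs, SAEs, MRI data and changes in concomitant medications (CM"). The safety entry in the protocol synopsis likewise lists "urinalysis, AEs, and changes in concomitant medications". Protocol 9.1.1 words it differently, as "requirement of concomitant medications".

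**The definitions.** Protocol 6.2: "Concomitant medications are those given to the subject during or after the first transplantation". There is no condition on start date or change of dose. SAP Appendix I 3.4 defines a prior medication as "any medication taken prior to the date of first treatment and either stopped prior to the first treatment or continued after it". SAP 6.8.1 treats a medication with a completely missing end date as concomitant.

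**The planned summaries.** SAP 7.7 codes all medications to ATC level 2 and preferred term, and then: "Separate Tables will display prior medications and CMs using the Safety Population". It adds: "The displays of medications will be performed without any regard to the indication the medication was taken for". Neither SAP section 8 nor section 4 of Appendix I plans a summary of medications started, stopped or changed in dose after first treatment.

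**The concern.** A table headed concomitant medications will be read as reporting on this endpoint component, but it counts use, not change. A participant who goes on taking a long-standing drug looks the same in it as one who first needed that drug after a lumbar puncture. The other quantitative components are handled differently: laboratory values get change from baseline and shift tables (SAP 8.3), and vital signs get change from baseline (SAP 8.4).

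Safety is the primary objective, participants receive three intrathecal administrations, and the results are meant to inform a later randomized study (SAP 4.3). New medication after dosing is useful tolerability information. As planned, a reader would have to extract it from listings.

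**Working it through.** The documents give no figure on this point, so there is none to reproduce. The check is of definitions, followed by illustrations on assumed values with n = 20 (SAP 4.3).

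**1. Where each kind of medication falls**

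| Medication history | Prior (Appendix I 3.4) | Concomitant (Protocol 6.2) |
|---|---|---|
| Stopped before first treatment | yes | no |
| Continued unchanged past first treatment | yes | yes |
| Continued, dose raised after first treatment | yes | yes |
| Newly started after first treatment | no | yes |

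Rows 2 and 3 cannot be told apart in either table. Rows 2 and 4 share the concomitant table.

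**2. Subtracting the tables does not isolate new starts.** For one row, let C be participants who continue, S those who stopped before dosing and did not restart, and N those not previously on it who start after dosing. Then prior = C + S, concomitant = C + N, and the difference is N − S. With assumed C = 12, S = 4, N = 4, both tables read 16/20 (12 + 4) and the difference is 0, although 4/20 started. Exact equality is a special case, but the difference is always net of stops.

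**3. How far a class row moves.** Let b be the share carrying a drug of the class past dosing, and r the share starting a drug of that class after dosing, independent of b. The concomitant share is b + (1 − b)r. A table of new starts shows r. Both b and r are assumed.

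| b | Concomitant row, r = 0 | Concomitant row, r = 0.5 | New-start table, r = 0 → 0.5 |
|---|---|---|---|
| 0.3 | 6/20 (30%) | 13/20 (65%) | 0/20 → 10/20 |
| 0.5 | 10/20 (50%) | 15/20 (75%) | 0/20 → 10/20 |
| 0.9 | 18/20 (90%) | 19/20 (95%) | 0/20 → 10/20 |
| 1.0 | 20/20 (100%) | 20/20 (100%) | 0/20 → 10/20 |

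For example, at b = 0.9 and r = 0.5: 0.9 + 0.1 × 0.5 = 0.95. The masking is severe only where carried-over use is common; at b = 0.3 the row still moves by 35 points.

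**4. Class row against preferred-term row.** Suppose 12 of 20 take a chronic drug of one class and all 12 add a second drug of that class that nobody took before. The class row reads 12/20 in both tables. The second drug's preferred-term row goes from 0/20 in the prior table to 12/20 in the concomitant table, so the addition can be seen there. If instead all 12 raise the dose of the drug they already take, neither row moves.

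**5. Date imputation.** SAP 6.8.1 moves a partial start date to the day of first treatment when the known month and year, or the year alone, match the start of treatment. A chronic drug recorded only with the treatment year would then appear to start on the first treatment day. The error runs one way, towards false new starts. SAP 6.8.1 gives no rule for a medication whose start date is completely missing.

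**The case against.** A reader might infer that this component of the primary endpoint cannot show harm. The documents do not support that.

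- SAP 6.1 requires subject listings of the safety data collected. With 20 participants, new starts can be read line by line.
- The preferred-term rows would show a newly used drug that few took before (step 4).
- An event needing treatment should also reach the adverse event output. Protocol 7.1.1 covers procedure-related observations, SAP 8.1 and 8.2.1 summarize procedure-related events separately, and Appendix I 4.1 keeps listings where it drops such tables.

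These points stand, and they limit the concern to how well the summaries separate new need from chronic use. A listing is still not a summary of a named endpoint component.

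A second argument is that Appendix I 3.4 makes continued drugs prior only, leaving just new starts in the concomitant table. The text does not say so: the Appendix does not redefine concomitant, Protocol 6.2 stands, and the SAP 6.8.1 default turns on the end date. Display in both tables is nevertheless an inference from the definitions, because the table shells are not in the documents.

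Third, the Protocol 9.1.1 wording, requirement, fits a plain concomitant table better than the wording on change does. That is fair, but the SAP and the synopsis both say change.

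Finally, it would be wrong to assume that every participant enters on disease-modifying therapy. Inclusion criterion 6 asks for a stable dose of permitted therapy; it does not establish that all take one.

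**Conclusion.** The mismatch is real and modest. The endpoint names change, while the planned tables report prevalence. Under the stated definitions a concomitant row can lie anywhere from 0/20 to 20/20 with no change after dosing. That range follows from the definitions alone; every intermediate figure above rests on assumed baseline use and assumed new starts.

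This does not undermine the primary safety assessment. The component is one of several in a descriptive, uncontrolled endpoint with no test or decision rule attached, and the underlying data will be listed. The added table is a cheap improvement that makes the summary match the endpoint. A reader might expect it to show that treatment caused new medication need. It could not, because the study has one arm and no control; it would describe need after dosing only.

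**What to change.** Add to SAP 7.7 one descriptive table on the Safety Population, by ATC level 2 and preferred term, giving the number and percentage of participants with:

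- any medication newly started on or after first treatment;
- where recorded, any dose increased or any medication stopped after first treatment;
- a separate row for medications started for an adverse event or procedure, where the indication is recorded.

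Exclude medications continued unchanged, and keep the two existing tables as background.

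Do not let the SAP 6.8.1 start-date imputation by itself make a drug new. Treat any medication recorded at the Visit 1, Visit 2 or pre-dose Visit 3 medication review as pre-existing; those reviews are already in the protocol schedule. Footnote records with partial or missing start dates that remain ambiguous.

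The cost is one extra table from medication data already being collected, and possible misclassification of a few records with partial dates. The documents do not show whether dose and indication are captured for every record, so those rows are conditional.

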7.7.1. Missing and Partial Concomitant and Other Medication Start and Stop Dates

Missing or partial Concomitant and Other Medication Start and Stop Dates will be imputed as described in [Section 6.8.1](#).

7.8. Exposure and Compliance to Study Drug

A summary of the number of IT administrations received will be presented using counts and percentages for the Safety Population.

The duration in months (exposure) between the first and third IT administration will be presented using descriptive statistics for the Safety population.

Compliance rate (%) will be calculated for each subject as follows:

$$(\text{Total number of IT administrations}) / (\text{Expected number of administrations}) * 100.$$

8. SAFETY AND TOLERABILITY

All safety analyses will be based upon the Safety Population.

All AEs will be coded to SOC and PT using the MedDRA, version 21.1.

A Treatment-emergent adverse event (TEAE), referred to subsequently as just TEAE or AE is an AE that occurs for the first time after initiation of first treatment or if it had occurred prior to initiation first treatment, it worsens in severity after initiation of first treatment.

AE's that occur prior to initiation of first treatment will only be in the listings and not included in any summary Tables.

AE's related to the Bone Marrow Aspiration will be included in a separate listing.

When evaluating changes in continuous safety parameters (such as laboratory measurements, vital signs, ECGs, etc.) , Baseline will be defined as the last measurement prior to first transplantation (i.e., prior to initiation of treatment).

Additional details for analysis of safety data are detailed below.

8.1. Overall Summary of Tolerability

The overall summary of tolerability table will present data by the NurOwn® group. Entries in this table will include:

1. Number of TEAEs
2. Subjects with at least one
 - a. Adverse event including procedure related AEs
 - b. Procedure related AEs
 - c. AE excluding procedure related AEs
 - d. AE related to the study medication
 - e. Severe AEs including procedure related Severe AEs
 - f. Severe AEs related to procedure
 - g. Severe AEs excluding procedure related Severe AEs
 - h. Severe treatment related AEs
 - i. Serious AEs
 - j. Serious treatment related AEs
 - k. AEs leading to study discontinuation
 - l. MS relapses
 - m. AEs leading to death

The above summaries will include the number of events as well as number and percentage of subjects experiencing at least one TEAE.

The subject data listing provides a complete list of all AEs as recorded in the CRF and supports this table and all other AE summary table subsets.

8.2. Adverse Event Preferred Term and Body/Organ System Summary Tables

Each Table will display the number and percentage of subjects who experience AEs with rows displaying the MedDRA primary SOC and PT. A subject who experiences multiple TEAEs coded to the same PT within the same SOC will be counted only once for that PT (or SOC for SOC rows). The number and percentage of subjects experiencing any TEAE will also be provided with each subject being counted only once. All percentages will use the number of subjects in the safety population as the denominator. Unless otherwise specified, in the summary Tables, SOCs will be sorted by alphabetical order and within SOC by PT alphabetically.

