3. STUDY OBJECTIVES AND ENDPOINTS

3.1. Study Objectives

3.1.1. Primary Objective

The primary objective of the study is to evaluate safety and tolerability of 3 intrathecal doses of NurOwn® (MSC-NTF cells).

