4.3. Sample Size Considerations

No formal sample size calculation is performed. Efficacy and safety data on 20 subjects will provide information to inform the design of a future randomized clinical study.

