8.4. Vital Signs

Mean Changes and % Changes from baseline to each post baseline timepoint in each Vital Signs assessment will be summarized along with other descriptive statistics for continuous variables.

Additionally, vital signs parameters will be categorized as low, normal or high according to the following ranges for clinically notable vital sign abnormalities

VITAL SIGNS		NOTABLE ABNORMALITIES Change Relative to baseline or Absolute Levels
Pulse (beats/min)		Either ≥ 120 + increase ≥ 15 or > 130 Either ≤ 50 + decrease ≥ 15 or < 40
Blood pressure (mmHg)	Systolic	Either ≥ 180 + increase ≥ 20 or > 200 Either ≤ 90 + decrease ≥ 20 or < 75
	Diastolic	Either ≥ 105 + increase ≥ 15 or > 115 Either ≤ 50 + decrease ≥ 15 or < 40
Weight		Either \leq or $\geq 10\%$ -

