9. EFFICACY

9.1. General Considerations

Descriptive statistics for continuous and categorical variables will be presented as described in [Section 6.4](#).

Inferential statistical tests will be performed at Type I error $\alpha = 0.05$ (Two-sided). Since this is a single arm, open label study, hypothesis testing will be performed against a historical database by selection of subjects matched on key screening or baseline characteristics.

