Total administration time should be approximately 5 minutes. Activities are rated by participant from 1 (not at all) to 5 (extremely) and summed to calculate a total score using a scale from 0 to 60 (ranging from low to high impact on walking). This score is then divided by 60 and multiplied by 100 to get a score between 0 and 100.

If a subject completes at least 6 items out of 12, the score is considered valid, otherwise if less than 6 items are completed the total score is considered missing.

If a subject does not complete all 12 items but does complete at least 6 items their total score is divided by the maximum score for the items completed and multiplied by 100.

Physical Activity as Measured by ActiGraph's CenterPoint Insight Watch (CPIW)

ActiGraph's CPIW (Wrist Sensor) is a medical-grade wearable physical activity, mobility, and sleep behavior monitoring FDA 510(k) cleared Class II medical device used for clinical research.

It will be issued to eligible subjects at Visit 1 with instructions on its use. The device is to be worn on the wrist of the non-dominant hand, throughout the duration of the study. The device will be returned to the site at Visit 7, the final study visit.

Subjects have the option to either take it off while they sleep or keep it on. It is water resistant so may be worn during showering.

The device contains an accelerometer and measures movements on the X, Y and Z coordinates.

These are then converted to various measures of physical activity, mobility and sleep quality. The device will allow to measure changes in mobility and physical activity following each treatment.

Analysis will include changes and % changes from baseline to each post baseline timepoint as well as between prior to each treatment and each week following it. Due to outliers, analyses may be performed including and excluding outliers.

Baseline will be the average of valid data from up to 7 days prior to the first treatment (V3), excluding the day of treatment.

Pre-treatment assessments will be the average of valid data from up to 7 days prior to the second (V4) and third treatments (V5), excluding the days of treatment.

Post treatment assessments will be based upon the average of valid data from each 7-day interval following each treatment visit (not including the day of visit).

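### No planned adverse-event table is split by dose, and vital-sign changes after doses 2 and 3 are flagged against the value before dose 1, although the primary objective is tolerability of three doses

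*SAP*

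**What the plan says.** SAP 3.1.1 sets the primary objective: to "evaluate safety and tolerability of 3 intrathecal doses of NurOwn". Protocol 1.1.1 agrees.

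**Adverse events.** SAP 6.1 puts all subjects in one treatment column. SAP 8.2 states: "A subject who experiences multiple TEAEs coded to the same PT within the same SOC will be counted only once for that PT". It adds: "All percentages will use the number of subjects in the safety population as the denominator". Under SAP 6.5.1 that population requires only one transplantation. In the severity tables of SAP 8.2.1 a subject appears once, at the maximum severity. SAP 8.1 also gives numbers of events, and Protocol 9.3.5 asks for numbers of events and of participants by SOC and PT. None of these outputs is by dose or by interval after a dose. Appendix I, section 4.1, drops some adverse-event tables and adds none by dose.

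**Vital signs.** Protocol 4.7.1, 4.7.3 and 4.7.5 and SAP Table 3 schedule readings before each transplantation and at 2, 8, 20 and about 24 hours after it. For continuous safety parameters SAP 8 says: "Baseline will be defined as the last measurement prior to first transplantation (i.e., prior to initiation of treatment"). SAP 8.4 plans "Mean Changes and % Changes from baseline to each post baseline timepoint in each Vital Signs assessment", and its notable-abnormality rules combine an absolute level with a change from that baseline, or use a more extreme absolute level alone.

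**Wearable device.** For this secondary endpoint, SAP 9.6 does plan a per-treatment reference: changes from baseline "as well as between prior to each treatment and each week following it".

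**The concern.** Protocol 2.1 says the three completed trials showed the safety of a single dose, and that three repeat doses are under test in an ongoing ALS trial. Whether tolerability holds up over doses 2 and 3 is thus a natural part of the primary objective here. Data collection follows the doses: there is monitoring around each transplantation and a telephone review of adverse events 1 to 2 weeks after each. The adverse-event tables drop that structure.

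For vital signs, a reading two hours after dose 2 is judged against one taken about 8 weeks earlier, and after dose 3 about 16 weeks earlier. Drift between visits then mixes with any acute reaction. A flag can be missed or raised wrongly, in the outputs that serve the primary objective.

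**Working it through.** There is no stated figure to reproduce. SAP 4.3 says "No formal sample size calculation is performed", and no safety test, margin or precision is given; the two-sided 0.05 level in SAP 9.1 ("Inferential statistical tests will be performed at Type I error") appears under efficacy. The risks and readings below are illustrations. The rules applied to them are the SAP's.

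**1. Once-per-subject incidence.** With independent per-dose risks p1, p2, p3 and all 20 subjects given three doses, incidence = 1 - (1-p1)(1-p2)(1-p3). If each dose causes at most one event, expected total events = 20 × (p1+p2+p3).

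| Pattern | Per-dose risk | Incidence | Subjects of 20 | Events |
|---|---|---|---|---|
| Flat | 10/10/10% | 1 - 0.90×0.90×0.90 = 27.1% | 5.4 | 20×0.300 = 6.0 |
| Rising | 2/8/19.1% | 1 - 0.98×0.92×0.809 = 27.1% | 5.4 | 20×0.291 = 5.8 |
| Falling | 20/7/2% | 1 - 0.80×0.93×0.98 = 27.1% | 5.4 | 20×0.290 = 5.8 |

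The three patterns give the same incidence and nearly the same total event count.

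**2. Missed flag.** The SAP 8.4 low systolic rule is 90 or less with a fall of at least 20, or below 75. Take 100 before dose 1, 130 before dose 2 and 88 two hours after dose 2.
- Against the pre-dose-1 value: 88 - 100 = -12. The fall is under 20 and 88 is not below 75, so there is no flag.
- Against the same visit: 88 - 130 = -42. Flagged.

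**3. Invented flag.** The high pulse rule is 120 or more with a rise of at least 15, or above 130. Take 104, 108 and 122.
- Against the pre-dose-1 value: 122 - 104 = +18. Flagged.
- Against the same visit: 122 - 108 = +14. Not flagged.

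**4. What the by-timepoint means can recover.** (post - baseline) - (pre - baseline) = post - pre. With pulse 70, 80, 82 the planned changes are +10 and +12, and the difference is the acute change, +2. With 80, 66, 82 they are -14 and +2, and the acute change is +16. The mean acute change is therefore recoverable if the pre-dose reading is tabulated as its own timepoint on the same subjects. SAP 8.4 does not say that it is. Appendix I, section 3.1, speaks of tables by visit, and SAP 6.7.4 takes the most abnormal value when abnormalities are summarised by timepoint. The standard deviation of the acute change, and flags against the pre-dose value, cannot be recovered from means.

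**5. A naive by-dose split would mislead.** Follow-up is about 8 weeks after doses 1 and 2 and 28 - 16 = 12 weeks after dose 3. A constant hazard giving 10% per 8 weeks gives 1 - 0.9^(12/8) = 14.6% over 12 weeks, an apparent rise with no dose effect.

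**6. What 20 subjects can show.** For an exact McNemar test of dose 1 against dose 3 (two-sided 0.05, responses independent within subject), power is 18.8% for a rise from 10% to 30% and 69.4% for a rise to 50%. The table can only be descriptive.

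**The case against.** A reader might infer that all safety data are pooled over doses and that a repeat-dose effect cannot be seen at all. The documents do not support that.

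- Vital-sign and laboratory summaries are by timepoint (SAP 8.3, 8.4). Only the adverse-event tables and the laboratory shift table are pooled.
- Event counts are planned. If 20 subjects had an event after one dose, or after all three, the counts would be 20 against 60. They would not show which dose the events followed.
- SAP 6.7.2 and 6.8.1 presuppose adverse-event dates, and the listings carry all recorded data, so events in 20 subjects can be assigned to doses by hand.
- Discontinuation by number of treatments (SAP 7.1) and failure to receive the next dose (Appendix I, section 3.6) are summarised.

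A reader might also infer a large denominator error. Four subjects with an event after dose 3 would be 4/20 = 20% on the full population but 4/14 = 28.6% if only 14 reached dose 3. That attrition is an assumption, and the plan prints no row for events after dose 3. Appendix I, section 2, calls the difference between the EE and mITT populations minimal, and EE requires all three treatments, so few mITT subjects probably missed a dose. The mITT set may still be smaller than the safety set.

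Finally, a single pre-treatment baseline is the protocol's own rule (9.3.5) and is valid for cumulative change; whole-course incidence is a legitimate answer to the objective as written; and the table shells and DSMB outputs are not among these documents.

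All of this stands and limits the point. It does not supply a prespecified by-dose summary of adverse events, nor a vital-sign flag that isolates the acute change.

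**Conclusion.** The point holds in limited form. No listed adverse-event table shows tolerability by dose, and the incidence tables cannot distinguish rising from falling risk, even if every subject receives all three doses. The acute vital-sign flag after doses 2 and 3 uses a reference 8 or 16 weeks old and, by its printed rule, can err in both directions. The risks and readings are illustrations, so they show that the outputs can mislead, not how often they will. The information can largely be rebuilt from listings and by-timepoint means. This is a worthwhile, cheap improvement to the primary analysis, not a flaw that defeats it.

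**What to change.** 1. **SAP 8.2.1.** Add one descriptive TEAE table by most recent dose: subjects and events, by SOC and PT and by maximum severity within the interval, with subjects given that dose as denominator. Use an equal window after each dose, cut off at the next dose, or events per person-week. Six weeks is one choice: under Protocol 2.1 the shortest gap is 8 weeks less 14 days. Protocol 4.7.5 times dose 3 from dose 1, which would allow a gap of 14 - 10 = 4 weeks between doses 2 and 3, and footnote 12 of Protocol Table 1 allows more flexible windows. The cut-off is therefore needed, and person-time is the safer choice.
2. **SAP 8.4.** For the 2 to 24 hour readings at Visits 3, 4 and 5, compute change and the existing notable-change criterion against the same visit's pre-dose reading. Keep the pre-dose-1 baseline alongside for cumulative change.
3. **SAP 6.2 and 6.4.** Reconcile their references to columns by dose and to a dose-group denominator with the single group in SAP 6.1 and the denominator in SAP 8.2. No dose groups are defined.

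**Cost.** SAP wording and two extra outputs with small counts, labelled descriptive. This assumes that the eCRF, which is not among the documents, holds adverse-event onset dates, and onset times on transplantation days.
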